4.4.1.2 Statistical Hypothesis, Model, and Method of Analysis

The primary analysis is the comparison of number of bleeding sites at 6 weeks between the following study products:

- Experimental Dentifrice versus (vs) Negative Control Dentifrice

Experimental Dentifrice: 67% w/w sodium bicarbonate, 0.2% w/w high molecular weight sodium hyaluronate and 0.221% w/w sodium fluoride

208175

Final Version 1.0 Statistical Reporting and Analysis Plan Text (Amendment 1),
10 Jun 2021

The NBS at 6 weeks will be analyzed using an Analysis of Covariance (ANCOVA) model with study product group and gender as factors and baseline NBS as covariate. Note that since the baseline NBS will be included as a covariate, the NBS stratification value will not be included in the model.

The null hypothesis for the primary endpoint is that there is no difference in the NBS between the experimental product and the negative control study product groups.

H₀: $\mu_1 = \mu_2$

The alternative hypothesis is that there is a difference in the NBS between the two study product groups.

H₁: $\mu_1 \neq \mu_2$

Using the above model, within-product adjusted means and corresponding SEs will be displayed with the study product group adjusted mean difference, SE, 95% confidence interval (CI) of the difference, between-product p-value and percent difference between study product groups in **CCI [REDACTED]** for mITT population.

Percent difference will be calculated as:

- Percent Difference = (Adjusted Mean Difference/Adjusted Mean of Negative Control Dentifrice) x 100.

All statistical tests of hypotheses will be two-sided and will employ a level of significance of $\alpha = 0.05$.

This study will be considered successful if a statistically significant difference between the adjusted mean NBS of the two study product groups at Week 6 is observed to be in favor of the Experimental Dentifrice.

The assumption of residual normality and variance homogeneity in ANCOVA analysis will be investigated through residual plots. If violated, data transformation or a nonparametric method (such as Van Elteren test adjusting for gender and baseline NBS stratification) will be used.

4.4.1.3 Supportive Analyses

If there is more than 10% difference in the overall number of subjects between PP and mITT populations, a summary of the primary efficacy variable will be presented for all subjects in the PP population (**CCI [REDACTED]**), mean and SE will be presented graphically over time (**CCI [REDACTED]**) and the same ANCOVA model applied to the primary analysis will be performed on the PP population (**CCI [REDACTED]**).

Experimental Dentifrice: 67% w/w sodium bicarbonate, 0.2% w/w high molecular weight sodium hyaluronate and 0.221% w/w sodium fluoride

208175

Final Version 1.0 Statistical Reporting and Analysis Plan Text (Amendment 1),
10 Jun 2021

4.4.2 Secondary Efficacy Variables

4.4.2.1 Number of Bleeding Sites at Week 6

The NBS at Week 6 (Visit 6) will be calculated in the same way as stated in [Section 4.4.1.1](#) for following product comparisons:

- Experimental Dentifrice vs Positive Control Dentifrice
- Positive Control Dentifrice vs Negative Control Dentifrice

4.4.3 Exploratory Efficacy Variables

For all statistical analyses described in subsections below, the assumption of residual normality and variance homogeneity in ANCOVA models will be investigated. Violation of this assumption will be overcome using a suitable data transformation or a non-parametric technique (e.g. Van Elteren test).

4.4.3.1 Number of Bleeding Sites at 3 Days, 1 and 2 Weeks

The NBS at 3 Days (Visit 3), Week 1 (Visit 4) and Week 2 (Visit 5) will be analyzed in the same way as stated in [Section 4.4.1.1](#) for the following product comparisons:

- Experimental Dentifrice vs Positive Control Dentifrice
- Experimental Dentifrice vs Negative Control Dentifrice
- Positive Control Dentifrice vs Negative Control Dentifrice

4.4.3.2 Mean BI at 3 Days, 1, 2 and 6 Weeks

Mean BI will be assessed at 3 Days (Visit 3), Week 1 (Visit 4), 2 (Visit 5) and Week 6 (Visit 6) for the following product comparisons:

- Experimental Dentifrice vs Positive Control Dentifrice
- Experimental Dentifrice vs Negative Control Dentifrice
- Positive Control Dentifrice vs Negative Control Dentifrice

In addition to the primary analysis based on the NBS, an analysis of gingival bleeding will be performed on the full BI. The mean BI score will be calculated taking the average over all tooth sites for a subject. The mean whole mouth BI score for each subject will be derived from the total BI score divided by the number of tooth sites scored. Refer to [Section 4.4.1.1](#) and [Table 4.2](#) for more details on BI.

Mean BI will be analyzed using ANCOVA model with product group, gender and number of bleeding sites strata as factors, and baseline BI score as covariate. Adjusted means for all products and all pairwise product differences will be provided along with 95% CI.

Experimental Dentifrice: 67% w/w sodium bicarbonate, 0.2% w/w high molecular weight sodium hyaluronate and 0.221% w/w sodium fluoride

208175

Final Version 1.0 Statistical Reporting and Analysis Plan Text (Amendment 1),
10 Jun 2021

4.4.3.3 Mean MGI at 3 Days, 1, 2 and 6 Weeks

The mean MGI at 3 Days (Visit 3), Week 1 (Visit 4), Week 2 (Visit 5) and Week 6 (Visit 6) will be analyzed for the following product comparisons:

- Experimental Dentifrice vs Positive Control Dentifrice
- Experimental Dentifrice vs Negative Control Dentifrice
- Positive Control Dentifrice vs Negative Control Dentifrice

The MGI will be assessed for the facial and lingual/palatal gingiva of all evaluable teeth, four sites per tooth (facial surface - papilla and margin; lingual/palatal surface - papilla and margin).

Mean MGI will be calculated taking the average over all tooth sites for a subject.

The MGI scoring system will be as described in [Table 4-3](#) and will be assessed by the same examiner on all evaluable teeth at 3 Days (Visit 3), Week 1 (Visit 4), Week 2 (Visit 5) and Week 6 (Visit 6).

Table 4-3 The Modified Gingival Index

Score	Description
0	Absence of inflammation
1	Mild inflammation: slight change in colour, little change in texture of any portion of the marginal or papillary gingival unit
2	Mild inflammation: criteria as [1] but involving the entire marginal or papillary gingival unit
3	Moderate inflammation: glazing, redness, edema, and/or hypertrophy of the marginal or papillary gingival unit
4	Severe inflammation: marked redness, edema and/or hypertrophy of the marginal or papillary gingival unit, spontaneous bleeding, congestion, or ulceration

The mean whole mouth MGI score for each subject will be derived from the total MGI score divided by the number of tooth sites scored.

The mean MGI score will be analyzed using ANCOVA with study product group, gender and number of bleeding sites strata as factors and baseline mean MGI score as a covariate. Adjusted means and their SEs for each study product group will be displayed with the study product group difference, SE, 95% CI of the difference, between-product p-value and percent difference between study product groups for mITT population.

4.4.3.4 Turesky Plaque Index (Overall and Interproximal) at 3 Days, 1, 2 and 6 Weeks.

The mean TPI (Overall and Interproximal) at 3 Days (Visit 3), Week 1 (Visit 4), Week 2 (Visit 5) and 6 Weeks (Visit 6) will be analyzed for the following product comparisons:

Experimental Dentifrice: 67% w/w sodium bicarbonate, 0.2% w/w high molecular weight sodium hyaluronate and 0.221% w/w sodium fluoride

208175

Final Version 1.0 Statistical Reporting and Analysis Plan Text (Amendment 1),
10 Jun 2021

- Experimental Dentifrice *vs* Positive Control Dentifrice
- Experimental Dentifrice *vs* Negative Control Dentifrice
- Positive Control Dentifrice *vs* Negative Control Dentifrice

Supra-gingival plaque will be assessed on the facial and lingual surfaces of the teeth using the Turesky Plaque Index (TPI). Each tooth surface will be divided into three areas; three scores will be recorded facially (mesiofacial, facial, distofacial) and three scores lingually (mesiolingual, lingual and distolingual) generating six scores per tooth. The plaque will be disclosed and scored for each site as follows:

Table 4-4 Turesky Plaque Index

Score	Description
0	No plaque
1	Separate flecks of plaque at the cervical margin
2	Thin continuous band of plaque (up to 1 mm) at the cervical margin
3	Band of plaque wider than 1 mm but covering < 1/3 of the tooth surface
4	Plaque covering \geq 1/3 but < 2/3 of the tooth surface
5	Plaque covering \geq 2/3 of the tooth surface

The mean Overall TPI score for each subject will be derived from the Total TPI score over all tooth sites divided by the number of tooth sites scored.

The mean Interproximal TPI score for each subject will be derived in the same way as for the overall scores but based on the mesiofacial, distofacial, mesiolingual and distolingual surfaces only.

The mean Overall TPI and mean Interproximal TPI scores will be analyzed using ANCOVA model with study product group, gender and number of bleeding sites strata as factors and baseline plaque score as covariate. Separately for Overall TPI score and Interproximal TPI score, adjusted means and their SEs for each study product group will be displayed with the study product group difference, SE, 95% CI of the difference, between-product p-value and percent difference between study product groups for mITT population.

4.4.3.5 Mean MGI and Mean BI at 3 days, 1, 2 and 6 Weeks within each subgroup (low and high number of bleeding sites)

Mean MGI and Mean BI at each visits will be analysed for the low and high NBS subgroup (Low NBS < 45, High NBS \geq 45) for the following product comparisons:

- Experimental Dentifrice *vs* Positive Control Dentifrice
- Experimental Dentifrice *vs* Negative Control Dentifrice
- Positive Control Dentifrice *vs* Negative Control Dentifrice

Experimental Dentifrice: 67% w/w sodium bicarbonate, 0.2% w/w high molecular weight sodium hyaluronate and 0.221% w/w sodium fluoride

208175

Final Version 1.0 Statistical Reporting and Analysis Plan Text (Amendment 1),
10 Jun 2021

Mean MG1 score will be analyzed using ANCOVA model with treatment group, gender and number of bleeding sites strata as factors, baseline MG1 score as covariate and NBS strata (Low and High NBS) into study product groups as interaction effect. Adjusted means for all treatments and all pairwise treatment differences will be provided along with 95% confidence intervals.

Mean BI will be analyzed using ANCOVA model with treatment group and gender and number of bleeding sites strata as factors, baseline BI score as covariate and NBS strata (Low and High NBS) into study product groups as interaction effect. Adjusted means for all treatments and all pairwise treatment differences will be provided along with 95% confidence intervals.

4.4.4 Handling of Missing Values/Censoring/Discontinuations

Missing data will not be replaced or imputed. Subjects who withdraw from the study early will be included in the statistical analysis up to the point of withdrawal. Subjects who withdraw will not be replaced.

4.5 Analysis of Secondary and Exploratory Objectives

Each secondary and exploratory variable will be analyzed separately. All analyses will be conducted on the mITT population only.

4.5.1 Analysis of Secondary Objectives

4.5.1.1 Number of Bleeding Sites at Week 6

Using the same methodology as described above for primary analyses, pairwise product differences will be provided along with 95% CI (CCI [REDACTED]) for the following product comparisons:

- Experimental Dentifrice vs Positive Control Dentifrice
- Positive Control Dentifrice vs Negative Control Dentifrice

The mean and SE of the NBS for each study product group will be presented graphically over time for the mITT population in CCI [REDACTED].

The BI obtained for each site along with the details of whether or not the site was bleeding (i.e. 'Yes' if BI score for a site is 1 or 2) and total number of bleeding sites will be listed by subject and visit in CCI [REDACTED] for all randomized subjects. Analysis of Exploratory Objectives

4.5.1.2 Number of Bleeding Sites at 3 Days, 1 and 2 Weeks

Using the same methodology as described above for primary analyses, pairwise product differences will be provided along with 95% CI (CCI [REDACTED]) for the following product comparisons:

Experimental Dentifrice: 67% w/w sodium bicarbonate, 0.2% w/w high molecular weight sodium hyaluronate and 0.221% w/w sodium fluoride

208175

Final Version 1.0 Statistical Reporting and Analysis Plan Text (Amendment 1),
10 Jun 2021

- Experimental Dentifrice vs Positive Control Dentifrice
- Positive Control Dentifrice vs Negative Control Dentifrice
- Experimental Dentifrice vs Negative Control Dentifrice

The mean and SE of the NBS for each study product group will be presented graphically over time for the mITT population in CCI [REDACTED].

The BI obtained for each site along with the details of whether or not the site was bleeding (i.e. 'Yes' if BI score for a site is 1 or 2) and total number of bleeding sites will be listed by subject and visit in CCI [REDACTED] for all randomized subjects.

4.5.1.3 Mean BI at 3 Days, 1, 2 and 6 Weeks

Summary statistics including n, mean, SD, SE, median, minimum, maximum will be provided by visit and randomized product group for the mITT population (CCI [REDACTED]). Mean BI will be analyzed using ANCOVA model in CCI [REDACTED] for mITT population.

Raw means and SE will also be plotted over time by product group (CCI [REDACTED]).

The mean whole mouth BI score will be listed by subject and visit in CCI [REDACTED] for all randomized subjects.

4.5.1.4 Mean MGI at 3 Days, 1, 2 and 6 Week

Descriptive statistics (n, mean, SD, SE, median, minimum, maximum) of the mean MGI score will be provided by visit and randomized study product group for the mITT population (CCI [REDACTED]). The mean MGI score will be analyzed using ANCOVA model in CCI [REDACTED] for mITT population.

The raw mean and SE of the MGI score will be presented graphically over time by study product group for the mITT population in CCI [REDACTED].

The MGI obtained for each tooth, surface and site will be listed by subject and visit in CCI [REDACTED] for all randomized subjects. The mean whole mouth MGI score will be listed by subject and visit in CCI [REDACTED] for all randomized subjects.

4.5.1.5 Mean TPI (Overall and Interproximal) at Day 3, 1, 2 and 6 Weeks

Descriptive statistics (n, mean, SD, SE, median, minimum, maximum) of the mean Overall TPI score (CCI [REDACTED]) and mean Interproximal TPI score (CCI [REDACTED]) will be provided by visit and study product group for the mITT population.

Results from ANCOVA analyses will be presented in CCI [REDACTED] (mean Overall TPI score) and in CCI [REDACTED] (mean Interproximal TPI score) for the mITT population.

Experimental Dentifrice: 67% w/w sodium bicarbonate, 0.2% w/w high molecular weight sodium hyaluronate and 0.221% w/w sodium fluoride

208175

Final Version 1.0 Statistical Reporting and Analysis Plan Text (Amendment 1),
10 Jun 2021

The raw mean and SE of the Overall TPI score for each study product group will be presented graphically over time for the mITT population in CCI [REDACTED].

The TPI obtained for each tooth, surface and site will be listed by subject and visit in CCI [REDACTED] for all randomized subjects. The mean Overall TPI score and mean Interproximal TPI score will be listed by subject and visit in CCI [REDACTED] for all randomized subjects.

4.5.1.6 Mean MGI and Mean BI at 3 days, 1, 2 and 6 weeks within each subgroup (low and high number of bleeding sites)

Mean MGI and Mean BI will be analysed in the same way as described in [Section 4.4.3.5](#) or the subgroup of low and high number of bleeding sites (Low NBS < 45, High NBS \geq 45) and summary will be presented in CCI [REDACTED] and CCI [REDACTED], respectively for the subgroup of low and high NBS for mITT population.

Mean MGI for low and high NBS will be analysed the same way as described in [Section 4.4.3.5](#) or all visits (CCI [REDACTED]). The raw mean and SE of the Mean MGI score for each NBS group will be presented graphically over time by study product group in CCI [REDACTED].

Mean BI for low and high NBS will be analysed the same way as mentioned in [Section 4.4.3.5](#) for all visits (CCI [REDACTED]). The raw mean and SE of the Mean BI score for each NBS group will be presented graphically over time by study product group in CCI [REDACTED].

4.6 Analysis of Safety

All safety data will be reported for the Safety population as per actual study product received. The safety profile of the study products will be assessed with respect to AEs, incidents, Oral Soft Tissue (OST) examination and Oral Hard Tissue (OHT) examination.

4.6.1 Adverse Events and Serious Adverse Events

All AEs will be reviewed by the Clinical Research Scientist or Designee prior to database lock and will be coded to a system organ class (SOC) and preferred term (PT) using the Medical Dictionary for Regulatory Activities (MedDRA).

AEs will be classified as oral and non-oral on the AE page of the electronic CRF.

Treatment emergent adverse events (TEAEs) are defined as AEs with an onset date/time on or after the date/time of first study product use. AEs with an onset date/time prior to the first study product use will be considered as non-treatment emergent.

The following summary tables and listings will be presented by study product group:

- Table of TEAEs by system organ class (SOC) and Preferred Term (PT) (CCI [REDACTED]).
- Table of TEAEs by Oral/Non-Oral and PT (CCI [REDACTED]).

Experimental Dentifrice: 67% w/w sodium bicarbonate, 0.2% w/w high molecular weight sodium hyaluronate and 0.221% w/w sodium fluoride

208175

Final Version 1.0 Statistical Reporting and Analysis Plan Text (Amendment 1),
10 Jun 2021

- Table of treatment-related TEAEs by Oral/Non-Oral and PT (CCI [REDACTED]).
- Table of AEs related to COVID-19 by SOC and PT (CCI [REDACTED]).
- Listing of all AEs (CCI [REDACTED] for all randomized subjects; CCI [REDACTED] for non-randomized subjects).
- Listing of all AEs related to COVID-19 Subjects (CCI [REDACTED] for all screened subjects).
- Listing of incidents (CCI [REDACTED]).
- Listing of deaths (CCI [REDACTED]).
- Listing of non-fatal SAEs (CCI [REDACTED]).
- Listing of treatment-emergent AEs leading to study or drug discontinuation (CCI [REDACTED]).
- Listing of treatment-emergent AEs classified as oral (CCI [REDACTED]).

In the event that there is nothing to report, a null table or listing will be produced.

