1.1 Schedule of Activities

The schedule of activities table provides an overview of the subject visits and study procedures. The investigator may schedule visits (unplanned visits) in addition to those listed on the schedule of activities, to conduct evaluations or assessments required to protect the well-being of the subject.

Table 1-1 Schedule of Activities

Procedure/Assessment	Screening	Study Period				
		Visit 2 Day 0 ¹ Baseline	Visit 3 Day 3±1 days ¹	Visit 4 Day 7±2 (Week 1) ¹	Visit 5 Day 14±2 (Week 2) ¹	Visit 6 Day 42±3 (Week 6) ¹
Informed consent	X					
Demographics	X					
Medical History	X					
Prior/ current medications and treatments	X					
Oral soft tissue (OST) examination	X					
Oral hard tissue (OHT) examination	X					
Gross gingival assessment ²	X					
Urine pregnancy test ⁷	X					
Inclusion/ Exclusion Criteria	X					
Subject Eligibility	X					
Subject Continuance				X	X	X
Dispense washout dentifrice, toothbrush, diary & timer	X					
Oral hygiene instruction & supervised brushing with washout dentifrice	X					
Return washout products/ compliance checks		X				
Concomitant medications & treatments			X	X	X	X
Modified Gingival Index (MGI) assessment ³			X	X	X	X
MGI repeat assessment ³			X	X	X	X
Bleeding Index (BI) assessment			X	X	X	X
Plaque disclosure & Plaque Index (TPI) assessments			X	X	X	X
TPI repeat assessment ³			X	X	X	X

Washout Period: minimum 10 Days/ maximum 28 days

Stratification/randomization		X			
Sub- & supra-gingival prophylaxis with 2 nd examiner to confirm TPI=0 via plaque disclosure		X			
Dispense study products ⁴		X			
Collect study products, assess compliance and return to subject			X	X	X
Oral hygiene instruction & supervised brushing with study product at site		X	X	X	X
Return all study products to site					X
End of study dental prophylaxis (optional) ⁵					X
Adverse Events/ Incidents ⁸	X	X	X	X	X
Study Conclusion					X

Abbreviations: OST = Oral Soft Tissue; OHT = Oral Hard Tissue; MGI = Modified Gingival Index; BI = Bleeding Index; TPI = Turesky Plaque Index

Footnotes:

1. Subjects will abstain from overnight toothbrushing for a minimum of 12hrs (+6hr, -2hr) immediately prior to the assessment visits (Visits 2, 3, 4, 5 and 6)
2. In relation to the general dentition inclusion/ exclusion criteria
3. At least 2 repeatability assessments should be performed each day (≥ 1 in the morning; ≥ 1 in the afternoon)

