10 ADVERSE EVENT AND SERIOUS ADVERSE EVENTS

10.1 Definition of an Adverse Event (AE)

An AE is any untoward medical occurrence in a clinical study subject, temporally associated with the use of a study product including any washout or lead-in product (or medical device), whether or not considered related to the study product, including any washout or lead-in product (or medical device).

NOTE: An AE can therefore be any unfavorable and unintended sign (including an abnormal laboratory finding), symptom, or disease (new or exacerbated) temporally associated with the use of a study product including any washout or lead-in product (or medical device).

Events Meeting the AE Definition:

- Any abnormal laboratory test results (hematology, clinical chemistry, or urinalysis) or other safety assessments (e.g. ECG, radiological scans, vital sign measurements), including those that worsen from baseline, considered clinically significant in the medical and scientific judgment of the investigator (i.e., not related to progression of underlying disease).
- Exacerbation of a chronic or intermittent pre-existing condition including either an increase in frequency and/or intensity of the condition.

- New conditions detected or diagnosed after study product administration even though it may have been present before the start of the study.
- Signs, symptoms, or the clinical sequelae of a suspected drug-drug interaction.
- Signs, symptoms, or the clinical sequelae of a suspected overdose of either study product or a concomitant medication. Overdose per se will not be reported as an AE/SAE unless it is an intentional overdose taken with possible suicidal/self-harming intent. Such overdoses should be reported regardless of sequelae.
- "Lack of efficacy" or "failure of expected pharmacological action" per se will not be reported as an AE. Such instances will be captured in the efficacy assessments. However, the signs, symptoms, and/or clinical sequelae resulting from lack of efficacy will be reported as AE if they fulfill the definition of an AE.

Events NOT meeting the AE definition:

- Any clinically significant abnormal laboratory findings (if applicable) or other abnormal safety assessments which are associated with the underlying disease, unless judged by the investigator to be more severe than expected for the subject's condition.

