10.3 Reporting of Adverse Events

10.3.1 Reporting Period

All AEs, and therefore all SAEs will be collected immediately after a subject consents to participate in the study by the completion (signature) of the ICF and until 5 days following last administration of the study product (or last procedure).

Medical occurrences that began before obtaining informed consent will be recorded in the Medical History/Current Medical Conditions section of the CRF not the AE section.

Details recorded by the subject on a diary or similar document that meet the definition of an AE must also be discussed with the subjects and transcribed in the AE section of the CRF.

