10.6 Follow-up of Adverse Events

After the initial report, the investigator is required to proactively follow up with each subject and provide further information on the subject's condition.

All AEs (serious and non-serious) will be followed until resolution, until the condition stabilizes, until the event is otherwise explained, or until the subject is lost to follow-up.

The investigator is obligated to perform or arrange for the conduct of supplemental measurements and/or evaluations as may be indicated or as requested by GSK CH to elucidate as fully as possible the nature and/or causality of the AE. This may include additional laboratory tests or investigations, histopathological examinations, or consultation with other health care professionals.

New or updated information will be recorded on the AE CRF page and on the SAE form (subject to the classification of the AE).

The investigator will submit any updated SAE data to GSK CH within 24 hours of receipt of the information.

Investigators are not obliged to actively seek AEs in former subjects. However, if the investigator learns of a SAE, including death, at any time after a subject has been discharged from the study, and considers the event reasonably related to the study product or study participation, the investigator will promptly notify GSK CH by emailing the information to the GSK CH Clinical Operations Safety Reporting email box [PPD](#)). The GSK CH Study Manager or designee will be responsible for forwarding the information to the Case Management Group, Global Clinical Safety and Pharmacovigilance group mailbox at GSK [PPD](#)).

The investigator will submit any updated SAE data to GSK CH within the designated reporting time frames.

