12.2.7 Safety Analyses

All assessments of safety will be based on the safety population. Safety analyses will be performed according to the treatment that the subject received and will be coded using the Medical Dictionary for Regulatory Activities (MedDRA).

AEs will be collected immediately after a subject provides consent to participate in the study by the completion of the informed consent form. AEs will be regarded as treatment emergent if they occur on or after the first treatment application.

Treatment Emergent Adverse Events (by SOC/PT), Treatment Emergent Adverse Events (Oral/Non-Oral), Related Treatment Emergent AEs will be summarized by treatment.

Deaths, Non-fatal Serious Adverse Events, Treatment Emergent Adverse Events leading to study or drug discontinuation, Treatment Emergent Adverse Events Classified as oral, and incidents will be listed. The results of the OST and OHT examinations will be listed.

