To evaluate the efficacy of an experimental dentifrice containing 67% w/w sodium bicarbonate, 0.2% w/w HMW sodium hyaluronate and 0.221% w/w sodium fluoride compared to a 67% w/w sodium bicarbonate/ 0.221% w/w sodium fluoride dentifrice, with both compared to a fluoride control dentifrice, for the assessment of gingivitis, as measured by Modified Gingival Index (MGI), over 6 weeks twice daily use.	Mean MGI at 3 days, 1, 2 and 6 weeks.
To evaluate the efficacy of an experimental dentifrice containing 67% w/w sodium bicarbonate, 0.2% w/w HMW sodium hyaluronate and 0.221% w/w sodium fluoride compared to a 67% w/w sodium bicarbonate/ 0.221% w/w sodium fluoride dentifrice, with both compared to a fluoride control dentifrice, for the assessment of plaque accumulation, as measured by a Plaque Index (TPI; overall and interproximal), over 6 weeks twice daily use.	Mean TPI (overall and interproximal) at 3 days, 1, 2 and 6 weeks.
To evaluate and compare MGI and mean BI in low (<45 bleeding sites) and high (>45 bleeding sites) BI subgroups following twice daily use of an experimental dentifrice containing 67% w/w sodium bicarbonate, 0.2% w/w HMW sodium hyaluronate and 0.221% w/w sodium fluoride, a 67% w/w sodium bicarbonate/ 0.221% w/w sodium fluoride dentifrice and a fluoride control dentifrice, over 6 weeks twice daily use.	Mean MGI and mean BI at 3 days, 1, 2 and 6 weeks within each subgroup (low and high number of bleeding sites)
Safety	
To assess the oral tolerability of an experimental dentifrice containing 67% w/w sodium bicarbonate, 0.2% w/w HMW sodium hyaluronate and 0.221% w/w sodium fluoride, a 67% w/w sodium bicarbonate/ 0.221% w/w sodium fluoride dentifrice, and a fluoride control dentifrice over 6 weeks twice daily use.	Treatment-emergent adverse events over 6 weeks.

Experimental Dentifrice: 67% w/w sodium bicarbonate, 0.2% w/w high molecular weight sodium hyaluronate and 0.221% w/w sodium fluoride

208175

Final Version 1.0 Statistical Reporting and Analysis Plan Text (Amendment 1),
10 Jun 2021

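### Treatment-emergent AEs are defined by onset alone, so whether a pre-dose AE that worsens on product counts depends on how the site records it

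*SAP*

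**What the plan says.** The only safety endpoint is TEAEs: "Treatment-emergent adverse events over 6 weeks" (SAP 1.2). SAP 4.6.1 gives both sides of the rule:

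- Included: "Treatment emergent adverse events (TEAEs) are defined as AEs with an onset date/time on or after the date/time of first study product use".
- Excluded: "AEs with an onset date/time prior to the first study product use will be considered as non-treatment emergent".

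Protocol 12.2.7 is to the same effect: "AEs will be regarded as treatment emergent if they occur on or after the first treatment application". None of these sentences mentions an event that starts earlier and gets worse.

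Collection starts well before dosing. Protocol 10.3.1 says "All AEs, and therefore all SAEs will be collected immediately after a subject consents to participate in the study", and the Schedule of Activities gives "Washout Period: minimum 10 Days/ maximum 28 days".

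Two other parts of the protocol bear on worsening. Section 10.1 lists among the events that are AEs "Exacerbation of a chronic or intermittent pre-existing condition including either an increase in frequency and/or intensity of the condition". Section 10.6, on follow-up, says "New or updated information will be recorded on the AE CRF page and on the SAE form". Neither says which applies when an AE already on file from the washout worsens after first use.

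**The concern.** The study asks about oral tolerability, and a dentifrice can do harm by aggravating a soreness or lesion that is already there as well as by causing a new one. A rule that looks only at onset can miss the first kind of harm.

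What is at stake is the between-arm safety summary. Apart from the COVID-19 table, every AE table in SAP 4.6.1 is restricted to TEAEs. So are the listing of oral AEs and the listing of AEs leading to study or drug discontinuation. Two subjects with the same deterioration on the same product could fall on opposite sides of the endpoint because of a recording habit that neither document fixes.

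**Working it through.** No sample size, power or alpha depends on this definition, so there is no stated figure to reproduce. The check applies the written rule to worked cases.

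**Reference point.** Protocol 10.1 uses study product in a sense that takes in the washout product, whereas SAP 1.3 counts one washout product apart from three investigational/study products. The safety objective names only the three randomized dentifrices, so first use is read here as first use of the randomized dentifrice, Day 0.

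**Rule.** TEAE if onset date/time ≥ first use; otherwise not.

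| Case | Onset on the record | Result |
|---|---|---|
| (a) Starts Day −5, worsens Day +3, existing record updated | Day −5 | −5 < 0: not a TEAE |
| (b) Same event, worsening entered as a new AE | Day +3 | 3 ≥ 0: TEAE |
| (c) Complaint began before consent, worsening on Day +3 entered as an AE | Day +3 | 3 ≥ 0: TEAE |
| (d) Starts during Baseline probing or prophylaxis, worsens later, existing record updated | Day 0, before first brushing | Not a TEAE |

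Case (c) follows from Protocol 10.3.1: conditions that pre-date consent go to Medical History, so there is no AE record to update. Case (d) arises because the SAP uses date and time, and Protocol 8.2.1 puts the bleeding assessment and prophylaxis ahead of the first supervised brushing.

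**Which of (a) and (b) do the documents require?** Neither. Section 10.6 points towards (a), since it sends updated information to the AE page and gives no instruction to open a second record. Section 10.1 supports (b), but its exacerbation bullet covers chronic or intermittent pre-existing conditions. An acute AE that first appears in washout fits that wording least well. The oral soft and hard tissue rules (Protocol 9.3.1 and 9.3.2) do not settle the matter either, because their AE instruction refers to the Screening examination.

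**Size.** The documents give no AE rates. Purely as an assumption, let 5% to 20% of subjects have a pre-dose AE ongoing at first use, let 10% to 50% of those worsen, and let every case be recorded by route (a):

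- Per arm of 40: 40 × 0.05 × 0.10 = 0.2 to 40 × 0.20 × 0.50 = 4 subjects.
- Over 120: 0.6 to 12 subjects.
- Chance of at least one case among 120: 1 − (1 − 0.005)^120 = 45% at the low end, and almost 100% at the high end.

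The range is wide and rests wholly on the assumed rates.

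**The case against.** The strongest reply is that the existing text already works. If an exacerbation is itself an AE under Protocol 10.1, its onset is the date of worsening and the onset rule captures it. Section 10.6 is a general follow-up rule and does not forbid a new record. The CRF completion guidance, where this is usually settled, is not among the documents. This stands in part: it shows that the loss is not automatic. It does not show that the documents require the new record, and it is weakest for acute events.

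The second reply is that nothing disappears from the report. SAP 4.6.1 plans a listing of all AEs for randomized subjects, and the listings of deaths and non-fatal SAEs are not restricted to TEAEs. The soft tissue examination is repeated at every visit and listed, so a visible soft tissue change would also show there. A withdrawal would still appear with its reason in the disposition outputs (SAP 4.1.1). All of this stands. It limits the harm to the by-arm summaries and the two TEAE-restricted listings, which are what readers of the endpoint will use.

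The third reply is that eligibility is checked again at Baseline, with a full oral examination and an exclusion for severe oral conditions, so notable oral problems ongoing at first use should be uncommon. That is fair for washout events. It does not cover an event arising in the prophylaxis, which follows randomization.

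**Conclusion.** The point holds as a gap in the definition. An AE that begins after consent but before first use of the randomized dentifrice, and then worsens on product, can be classed as non-treatment-emergent. Whether it is depends on whether the site updates the old record or opens a new one.

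Two stronger readings should be resisted. A reader might infer that every such event is lost from the safety endpoint; Protocol 10.1 allows a route by which it is counted, so the documents do not support that. A reader might also take the washout's share of total AE-collection time as the size of the under-reporting. That share measures calendar time, whereas only AEs still ongoing at first use that then worsen are at issue. Their number cannot be estimated from the documents.

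The conclusion assumes that first study product use means the randomized dentifrice, and that no CRF guidance outside these documents already settles the recording. Efficacy analyses, sample size and alpha are unaffected. The change is worth making because TEAEs are the only safety endpoint and, with about 40 subjects per arm, a few oral events could alter the tolerability picture.

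**What to change.** In SAP 4.6.1 and Protocol 12.2.7, define a TEAE as an AE with onset on or after first use of the randomized dentifrice, or an AE with earlier onset that increases in intensity, or becomes serious, on or after that first use. Naming the randomized dentifrice also removes the doubt about the washout product.

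Implement it with a CRF completion note: such worsening is entered as a new AE record with its own onset date/time. The planned onset-based programming then picks it up unchanged, and the pre-dose record remains in the all-AE listing. For records already entered, the review of AEs before database lock that SAP 4.6.1 provides for is the place to find pre-dose AEs that worsened on product.

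The cost is one sentence in each document and one CRF note. The downside is a possibly slightly higher TEAE count.
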